#### **Alternative therapies**

Cover Letter:

All enclosed below documents are part of the clinical trial NCT03536819

Study Name: Radio-frequency rejuvenation for pelvic floor and vagina

Protocol No.: DO607404A

Document date: September 20, 2017

SPONSOR: InMode Ltd.

[name]

[name]

[name]

[name]

[contact]

[contact]

I. Data analysis.

A. Analysis Sets

1. Safety Analysis Set

a) The safety analysis set will include all subjects using Votiva procedures at least a single time.

2. Performance Analysis Set

a) Performance analysis set will consist of all subjects providing at least one post treatment performance measurement.

3. Treatment of Missing Values

a) Only observed data will be used; i.e. missing data will not be imputed.

B. Statistical Analysis

1. Means, and standard deviations for each characteristic will be calculated. Paired sample t-test will be computed to assess changes in before treatment and follow-up scores. Statistical significance will be calculated and two-tail significance level of 0.05 will be used. All analyses will be conducted using IBM SPSS 21.0.

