**Objective measurements:**

- Genitalia(vaginal and labia) condition and intentional muscle contraction will be evaluated at baseline, before each treatment and at follow up visits (8 weeks after each treatment). Visits 2, 4 and 6.

- Physical measurements of vagina, vulvar and perineal areas will be measured according to POP-Q guidelines. (Appendix 11.0) Visits 2, 4 and 6.

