**Subjective measurements:**

- - Subjective assessment of efficacy on sexual dysfunction symptoms, using the Female Sexual Function Index (FSFI) and Pelvic Organ Prolapse/Urinary

Incontinence Sexual Function Questionnaire (PISQ-12) questionnaire (Appendix 6.0, 9.0) at visits 1, 5 and 7.

- - Subjective assessment of efficacy on Urinary Incontinence symptoms using the International Consultation on Incontinence Questionnaire (ICIQ) and Questionnaire for Female Urinary Incontinence (QUID) (Appendix 7.0) at visits 1, 5 and 7.
- - Subjective assessment of quality of life change using Pelvic Floor Impact Questionnaire (PFIQ-7) (Appendix 8.0) at visits 1, 5 and 7.
- - Subjective assessment of improvement of pelvic organ prolapse, colorectal-anal disease or urinary distress as measured by the Pelvic Floor Distress Inventory Questionnaire (PFDI-20) (Appendix 10.0) at visits 1, 5, 7.

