**Study Duration**

Study duration for each subject is approximately four months (including screening, 2 treatment sessions 8 weeks apart and a follow-up visit at 8 weeks post last treatment.

Overall study duration will be approximately 12 months, depending on the subject recruitment rate.

Each subject will undergo 7 study visits including screening, 2 treatment and 1 follow-up visit.

**Visit 1:** Midwest Plastic Surgery-Evaluation

- Screening will be performed to determine subject eligibility as well as to collect all of the required medical information and obtain signed Informed Consent.
- Baseline photographs of the treatment area will be taken
- Pre-procedure questionnaires will be completed at this time
- Time required 1.5 hours

**Visit 2:** Antares Institute-Evaluation

- A complete pelvic floor assessment will be performed including but not limited to the following: measurement of internal and external pelvic floor contraction, measurement of vaginal canal length and diameter, measurement of the introitus, and length of the labia majora and minora. Measurements will be obtained following POP-Q protocol
- This visit will confirm inclusion criteria based on measurements.
- Time required: 1.5hrs

**Visit 3:** Midwest Plastic Surgery – 1st treatment

- Internal and external FormaV treatment
- Photographs of the treatment area will be taken after the procedure.
- Time required: 45 minutes

**Visit 4:** Antares Institute Follow-up visit – 8 weeks following first treatment

- A complete pelvic floor assessment will be performed including but not limited to the following: measurement of internal and external pelvic floor contraction, measurement of vaginal canal length and diameter, measurement of the introitus, and length of the labia majora and minora. Measurements will be obtained following POP-Q protocol.
- Time required: 15 minutes

**Visit 5:** Midwest Plastic Surgery – 2nd treatment

- Photographs of the treatment area will be taken before and after the procedure.
- Questionnaires will be completed.
- Time required: 45 minutes

**Visit 6:** Antares Institute Follow-up visit – 8 weeks following second treatment

- A complete pelvic floor assessment will be performed including but not limited to the following: measurement of internal and external pelvic floor contraction, measurement of vaginal canal

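### The SAP applies one unadjusted 0.05 to 13 protocol outcomes and gives none of them priority, so the stated 5% does not hold for the trial's efficacy conclusions.

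*SAP*

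**What the plan says.** The whole inferential plan is one paragraph, SAP section I.B.1. It opens with descriptive statistics: "Means, and standard deviations for each characteristic will be calculated". It then gives the test, "Paired sample t-test will be computed to assess changes in before treatment and follow-up scores", and the level, "Statistical significance will be calculated and two-tail significance level of 0.05 will be used". No outcome, visit, testing order or multiplicity adjustment is named.

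The protocol supplies the outcomes:

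- **Physical measures.** The visit list under Study Duration includes "measurement of internal and external pelvic floor contraction, measurement of vaginal canal length and diameter, measurement of the introitus", and also "length of the labia majora and minora". That makes seven: internal contraction, external contraction, canal length, canal diameter, introitus, labia majora and labia minora. The Objective measurements section schedules assessment "at follow up visits (8 weeks after each treatment). Visits 2, 4 and 6".
- **Questionnaires.** The Subjective measurements section lists six: FSFI, PISQ-12, ICIQ, QUID, PFIQ-7 and PFDI-20, each at Visits 1, 5 and 7.

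The protocol does rank its aims. Study Objectives names pelvic floor strength, measured by voluntary contraction, as primary and puts symptoms, quality of life and satisfaction second. The Primary Endpoints section, however, lists only visit completion and voluntary withdrawal.

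**The concern.** A two-sided 0.05 describes the error rate of one test. Here it is attached to many tests, and no rule says which of them decides whether the trial succeeded. The primary objective could provide that rule, but the SAP does not use it. The items headed Primary Endpoints are not efficacy variables, so they cannot provide it either.

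The same gap exists within single claims. FSFI and PISQ-12 both serve sexual function; the protocol introduces them together, "using the Female Sexual Function Index (FSFI) and Pelvic Organ Prolapse/Urinary" and so on. ICIQ and QUID serve urinary incontinence, and the PFDI-20 overlaps with them because its purpose is worded as alternatives: "Subjective assessment of improvement of pelvic organ prolapse, colorectal-anal disease or urinary distress as measured by the Pelvic Floor Distress Inventory Questionnaire (PFDI-20". Followed as written, the plan would let an effect be reported from whichever instrument or visit crossed 0.05. The stated 5% would then understate the chance that the reported effect is a false positive.

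**Working it through.** **Plan's own figure.** The only error rate in the documents is the per-test two-sided 0.05. The sample size (at least 20, under Patient Population and Sample Size) comes with no power, effect size or SD, so there is no power figure to reproduce.

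**Step 1: count the tests.** There are 7 physical measures and 6 questionnaires, 13 outcomes with each questionnaire counted once. The number of tests depends on what counts as follow-up:

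- One follow-up per outcome (Visit 6 or Visit 7): 7 + 6 = 13.
- Visits 4 and 6 for physical measures, Visit 7 only for questionnaires (Study Duration labels Visit 5 as the second treatment, not a follow-up): 7×2 + 6×1 = 20.
- Both post-treatment time points for everything: 7×2 + 6×2 = 26.

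**Step 2: chance of at least one p<0.05 if nothing changed, independent tests.** The formula is 1 − 0.95^k.

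- k = 13: 1 − 0.95^13 = 0.487
- k = 20: 1 − 0.95^20 = 0.642
- k = 26: 1 − 0.95^26 = 0.736

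The expected number of false positives is 0.05k, that is 0.65, 1.0 and 1.3, whatever the correlation.

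**Step 3: allow for correlation.** The documents give no correlations, so these are assumptions: a common correlation between outcomes, 0.5 between visits, and the product of the two across both. Two-sided paired t-tests were simulated with n = 20 and 40,000 null trials:

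| Correlation between outcomes | 13 tests | 20 tests | 26 tests |
|---|---|---|---|
| 0.3 | 42% | 56% | 64% |
| 0.5 | 35% | 48% | 55% |
| 0.7 | 25% | 37% | 41% |

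Smaller simulations at the same nominal correlations gave up to 66% and 43% for 26 tests at 0.3 and 0.7.

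**Step 4: the claims themselves, independent tests.**

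- Primary objective, internal and external contraction: final visit, 1 − 0.95^2 = 0.098; Visits 4 and 6, 1 − 0.95^4 = 0.185.
- Sexual function, FSFI and PISQ-12: one visit 0.098; two visits 0.185.
- Urinary symptoms, ICIQ, QUID and PFDI-20: one visit, 1 − 0.95^3 = 0.143; two visits, 1 − 0.95^6 = 0.265.

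Positive correlation lowers all of these.

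**Step 5: threshold for the fix.** At n = 20 the smallest significant mean change, in SDs of the change, is t(19)/√20.

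- Unadjusted 0.05: 2.093/4.472 = 0.47.
- Holm's first step over two readings, 0.025: 2.433/4.472 = 0.54.

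**The case against.** The strongest reply is that the protocol is not shapeless. It has one primary objective, and its Subjective measurements section ties each questionnaire to a domain. A reader might infer that nothing links results to claims, and that would be wrong. What is missing is the step from that ranking to the tests.

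A reader might also infer that there are at least 26 tests. The documents do not establish this as a minimum. The SAP names no visits, and Study Duration counts only one follow-up visit in its summary and calls Visit 5 a treatment visit. Conversely, Objective measurements treats the assessments after both treatments as follow-up, and Efficacy Endpoints compares results after the treatments with baseline. So 26 is a permitted reading, with 13 and 20 equally open.

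Nor do the documents show that a chance finding somewhere is more likely than not. That holds for 26 tests at low to moderate correlation and for 20 at low correlation. It fails for 13 tests, and for 26 at a correlation of 0.7. The any-result figure also includes measures such as labial length, so it is not the error rate of a claim about urinary symptoms or sexual function. For sexual function at the final visit alone, the rate is at most about twice 5%.

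It could also be said that a single small study is exploratory by nature. Neither document says so, and the SAP attaches a significance level to its comparisons. If the word scores in the SAP meant questionnaires only, there would be 6 or 12 tests (1 − 0.95^6 = 26%, 1 − 0.95^12 = 46%), and the primary objective would have no test at all.

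**Conclusion.** The point holds in this form: the SAP does not turn the protocol's ranking of objectives into a ranking of tests, so the stated 5% applies to each test but not to the trial's conclusions. The chance of at least one false positive exceeds 5% on every reading of the visits and every correlation examined here, from 25% (13 tests, correlation 0.7) to 74% (26 independent tests). For individual claims the excess is smaller, roughly two to five times 5% under independence and less with positive correlation.

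These figures assume that every named outcome is tested, that each questionnaire contributes one total score, and that the correlations are as set out. Subscales or individual POP-Q points, if tested, would add to the count. The defect is worth correcting because the correction is cheap. It does not make the planned measurements or the paired t-test unsuitable.

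**What to change.** Amend SAP section I.B.1 before the data are analysed:

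1. State that the only confirmatory test is the change in pelvic floor contraction from Visit 2 to Visit 6. Test the internal and external readings by the Holm procedure at an overall two-sided 0.05, or name one reading in advance and test it at 0.05. Either choice must be written down, because allowing whichever reading succeeds at 0.05 would run at about 10% under independence.
2. Report every other outcome, any subscales and the interim visits (4 and 5) as mean paired change with a 95% confidence interval, labelled exploratory, with no claim of significance.

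This needs SAP wording only: no extra subjects, visits or measurements. There are two costs. With Holm over two readings, the first step needs a mean change of 0.54 SD of the change at n = 20, against 0.47 SD unadjusted; naming one reading avoids this. The questionnaire results also lose the label of statistical significance, although their estimates and intervals are still reported in full.
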